Summary Table of Study Protocol

Title	Long Term Post Marketing Drug Use Result Survey for Blinatumomab in Japan
Protocol version identifier	1.0
Date of last version of the protocol	NA
EU Post Authorization Study (PAS) Register No	EUPAS29685
Active Substance	Blinatumomab
Medicinal Product	BLINCYTO
Product Reference	
Procedure Number	
Joint PASS	No
Research Question and Objectives	To investigate the incidence of CTCAE grade ≥ 3 events of each safety specification of the Japan Risk Management Plan (neurologic events, infections, cytokine release syndrome, tumor lysis syndrome, myelosuppression and pancreatitis) in patients receiving long term administration of blinatumomab
Country(ies) of Study	Japan
Author	PPD Manager, Post Marketing Surveillance, Global Patient Safety, Labeling & Pediatrics – Japan Amgen Astellas BioPharma K.K.

Approved

Marketing Authorization Holder

Marketing authorization holder(s)	PPD, President Amgen Astellas BioPharma K.K.
MAH Contact	PPD Senior Manager, Post Marketing Surveillance, Global Patient Safety, Labeling & Pediatrics – Japan Amgen Astellas BioPharma K.K. [name] Tel: PPD Fax: PPD E-mail: PPD

Confidentiality Notice

This document contains confidential information of Amgen Inc.

This document must not be disclosed to anyone other than the site study staff and members of the Institutional Review Board/Independent Ethics Committee/Institutional Scientific Review Board or equivalent, as applicable.

The information in this document cannot be used for any purpose other than the evaluation or conduct of the research without the prior written consent of Amgen Inc.

Approved

Study Design Schema

	At the time of registration	Cycle 6			Cycle 7 - 9		Safety follow-up
		Blinatumomab		Interval	Blinatumomab	Interval	
		Day 1 (Before treatment)	End of treatment/Day 29	Day 30 - 84	Day 1 - End of treatment/Day 29	Day 30 - 84	30 ± 3 days after the final treatment ¹
Registration	X						
Patient identification information	X						
Patient background		X ²					
Pregnancy/Lactation		X					X
Therapeutic history before blinatumomab		X ²					
Treatment of blinatumomab		X			X		
Concomitant medication/therapy				X			X
Adverse Event				X			X

Appendix C.	Sample Safety Reporting Form(s).....	32
Appendix D.	Additional Safety Reporting Information.....	34
Appendix E.	Pregnancy and Lactation Notification Worksheets.....	35

Approved

2. List of Abbreviations

Abbreviations	Definition of the Terms
AE	Adverse event
ALL	Acute lymphoblastic leukemia
BiTE	Bispecific T-cell engagers
CI	Confidence interval
CRF	Case report form
CRO	Contract research organization
CRS	Cytokine release syndrome
CTCAE	Common terminology criteria for adverse events
CTL	Cytotoxic T-lymphocyte
DFS	Disease-free survival
EC	Ethical committee
EDC	Electronic data capture
GPSP	Good Post-marketing Study Practice
HCPs	Health care professionals
ICJME	International committee of medical journal editors
J-NDA	Japan new drug application
J-PSUR	Japan periodic safety update report
J-RMP	Japan risk management plan
PMDA	Pharmaceuticals and medical devices agency
PMS	Post-marketing surveillance
Q	Quartile
SAP	Statistical analysis plan
SD	Standard deviation
TLS	Tumor lysis syndrome

3. Responsible Parties

Sponsor: Amgen Astellas BioPharma K.K., Japan

Collaboration partner: Astellas Pharmaceutical Inc., Japan

Contract Research Organization (CRO): EPS Corporation, Japan

Investigators: Investigators at medical institutions with active contracts for the survey,
Japan

4. Abstract

- Study Title
Long Term Post Marketing Drug Use Result Survey for Blinatumomab in Japan
- Study Background and Rationale
In the Japan new drug application (J-NDA) for blinatumomab, safety and efficacy data on 35 Japanese subjects were presented. The proposed post-marketing surveillance (PMS) will provide descriptive data from the real-world long term use of blinatumomab in patients in Japan to supplement the data in the J-NDA. Japan Risk Management Plan (J-RMP) includes this survey as a part of post-marketing pharmacovigilance activities.
- Research Question and Objective(s)
 - Primary Objective(s)
The primary objective of study is to investigate the incidence of CTCAE grade ≥ 3 events of each safety specification of the J-RMP (neurologic events, infections, cytokine release syndrome (CRS), tumor lysis syndrome (TLS), myelosuppression and pancreatitis) in patients receiving long term administration of blinatumomab.
 - Secondary Objective(s)
None
 - Hypothesis(es)/Estimation
There is no hypothesis to be tested. Instead, the proposed survey will provide descriptive data on real-world long term use of blinatumomab and adverse event occurrence in patients in Japan.
- Study Design/Type
Prospective observational study in post marketing setting without a comparator arm.
- Study Population or Data Resource
Patients for whom blinatumomab is prescribed at the cycle 6 to 9 at medical institutions
- Summary of Patient Eligibility Criteria
No exclusion criteria are applied.
- Follow-up
From the beginning of cycle 6 to the end of cycle 9
- Variables
 - *Outcome Variable(s)*
CTCAE grade ≥ 3 adverse events (including grade, seriousness and causal relations to drug)
 - *Exposure Variable(s)*
Daily dosage and duration of blinatumomab administration
 - *Other Covariate(s)*
Patient demographics and medical history, concomitant medication and therapy
- Study Sample Size

Approved

The planned number of patients in this survey was set to 40 patients.

- Data Analysis

Patient disposition, demographics and characteristics before cycle 1 will be summarized. The number of patients and the incidence rates of CTCAE grade ≥ 3 events are tabulated for each safety specifications and other adverse drug reactions during the survey.

5. Amendments and Updates

None

6. Milestones

Milestone	Planned date
Start of data collection	10 June 2019
End of enrollment	30 September 2022
End of observation	30 September 2023
End of data collection	30 September 2024
Final report of study results	31 March 2025

7. Rationale and Background

7.1 Diseases and Therapeutic Area

Acute lymphoblastic leukemia (ALL) is a heterogeneous hematologic disease characterized by the proliferation of immature lymphoid cells in the bone marrow and peripheral blood. Normal blood cell development in the marrow is therefore arrested and replaced with immature and abnormal lymphoblasts. The proliferation of these immature/abnormal lymphoid cells in the bone marrow subsequently crowd out the production of normal bone marrow elements ultimately resulting in decreased red blood cell, white blood cell and platelet counts (NCCN Clinical Practice Guidelines, 2014). ALL is a rare malignant disease with an overall incidence of 1.1/100,000 per year. ALL has a bimodal distribution with an early peak at 4 to 5 years of age (incidence of 4.5/100,000 per year) followed by a second gradual increase at 50 years (incidence of 2/100,000 per year). It represents 80% of acute childhood leukemia and 20% of acute leukemia cases in adults (Pui and Evans 1998; Jabbour et al, 2005; Larson, 2005; SEER, 1975-2009 [accessed July 2012]). ALL is also a rare disease in Japan. The overall incidence rate of all leukemia in 2007 was 4.9/100,000 (Cancer Statistics in Japan - 2012). The totals of all leukemia and adult cases in 2007 were 10,211 and 9,648, respectively (Cancer Statistics in Japan - 2012). ALL accounts for approximately 20% of adult leukemia cases (Naoe, 2003). Among ALL, acute childhood leukemia represents 80% and adult cases comprise 20%. In adult ALL, whereas previous studies in Japanese patients showed a

~80% CR rate by induction chemotherapy, 6-year survival rate remained 15% to 33% (Tanimoto et al, 1998; Ueda et al, 1998; Takeuchi et al, 2002). There are limited data in pediatric ALL in the relapsed/refractory setting specific to Japan. In frontline pediatric ALL, multi-agent chemotherapy based on BFM (Berlin-Frankfurt-Munster) group treatment regimen is the standard as in Western countries. While 5-year Disease-Free Survival (DFS) rates for standard and high-risk patients are approximately 85% and 70%, respectively, DFS in patients who did not respond to induction chemotherapy is less than 40%.

Blinatumomab belongs to a new class of bispecific antibody constructs called bispecific T-cell engagers (BiTE). BiTE has been designed to direct T cells towards target cells. The proximity induced by the BiTE triggers target cell-specific cytotoxicity, which closely resembles standard cytotoxic T-lymphocyte (CTL) activation. This T-cell-mediated target-specific killing is the therapeutic mechanism of action of blinatumomab (Löffler et al, 2000; Wolf et al, 2005). Blinatumomab was approved for patient with relapsed or refractory B-precursor ALL in Japan in September 2018. Patients will be received blinatumomab, administered continuous intravenous (cIV) infusion for a maximum of 9 treatment cycles. Blinatumomab was authorized as an orphan drug in Japan in October 2017.

7.2 Rationale

The safety and efficacy of blinatumomab for patients with relapsed or refractory B-precursor ALL has been demonstrated in the phase 1b/2 clinical trial of Japanese patients and global clinical trials. However, no observational study to examine the real-world long term use data of patients with relapsed or refractory B-precursor ALL has been conducted in Japan. Therefore, this study is set in J-RMP as a part of post-marketing pharmacovigilance activities to examine the safety for the real-world long term use of blinatumomab in patients with relapsed or refractory B-precursor ALL.

7.3 Statistical Inference (Estimation or Hypothesis[es])

There is no formal hypothesis to be tested. Instead, the proposed survey will provide descriptive data on real-world long term use of blinatumomab and adverse event occurrence in patients in Japan.

8. Research Question and Objectives

To obtain the safety information of the product in the real-world long term use of blinatumomab in Japan.

8.1 Primary

The primary objective of study is to investigate the incidence of CTCAE grade ≥ 3 events of each safety specification of the J-RMP in patients receiving long term administration of blinatumomab.

<Safety specification items to focus, as described in J-RMP>

- Important Identified Risks

Neurologic events, Infections, CRS, TLS, Myelosuppression, Pancreatitis

9. Research Methods

9.1 Study Design

This study is a non-interventional (observational) study of patients in Japan who will be treated with blinatumomab at the cycle 6 or later in the post-marketing setting without comparator arm.

9.2 Setting and Study Population

Patients for whom blinatumomab is prescribed in the cycle 6 or later at participating medical institutions will be registered without eligibility criteria, so that data can be collected on how blinatumomab will be used in Japan. This study targets the patients who started the blinatumomab cycle 6 therapy before concluding the contract with medical institutions, as well.

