9.2.3 Subject/Patient/Healthcare Professional Eligibility

9.2.3.1 Inclusion Criteria

Patients for whom blinatumomab is prescribed in the cycle 6 or later at medical institutions.

Approved

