9.2.6 Study Follow-up

Each patient will be followed from the beginning of cycle 6 to the end of cycle 9.

If administration of blinatumomab will be stopped or terminated between the beginning of cycle 6 and the end of cycle 9, the safety follow-up period shall be 30 ± 3 days after the final administration or up to the day before the implementation of hematopoietic stem cell transplantation or other antitumor therapy.

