9.3.3 Covariate Assessment

Following data are collected in patient registration form and CRF.

Approved

Patient information for registration: patient ID, sex, birth year/month, continuation status from 20170655 study, date of informed, start date of cycle 6 blinatumomab administration

Patient demographics and medical history (in case the patient is not continuing from 20170655 study): pregnancy/lactation, medical history (including central nervous system lesion or symptom, hepatic dysfunction and renal dysfunction), therapeutic history before blinatumomab administration to B-cell ALL, history of hematopoietic stem cell transplantation, Philadelphia chromosome examination

Pregnancy and lactation during observation period: birth (planned) years/month

Concomitant medication (excluding complication treatment medicine and CTCAE grade ≤ 2 adverse event treatment medicine): medicine name, duration, dosage

Concomitant therapy to primary disease: therapy name, duration

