9.5 Study Size

The targeted number of patients was set to 40 subjects to enable a consistent comparison and discussion on the safety during the maintenance phase in Japanese

patients and blinatumomab clinical trial (00103311 study) by collecting the information from the similar number of subjects as 36 subjects who underwent maintenance therapy of blinatumomab in 00103311 study. The incidence of CTCAE grade ≥ 3 neurologic events, infections and myelosuppression between cycles 6 and 9 in 00103311 study was 8.3% (3/36), 22.2% (8/36) and 16.7% (6/36) respectively. The collection of 40 subjects who transition to cycle 6 enables that the events with a true incidence of 8% or above are collected from at least 1 subject with 95% confidence, and thus a consistent evaluation for CTCAE grade ≥ 3 neurologic events, infections and myelosuppression is considered possible.

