9.9 Limitations of the Research Methods

This is a prospective, observational cohort study, so it has a limitation of internal validity and strength of external validity in comparison with an interventional clinical study. Limitations common to this type of study, along with how to reduce errors, are summarized below.

Limitations	How to reduce errors
Missing and incomplete data are unavoidable, because there are some cases that data could not be collected at all evaluation time points, and some patients could be lost to follow-up.	Efforts will be made to collect as complete data as possible and instructions to investigators. After examining the extent of missingness and incompleteness of study data, an appropriate statistical data imputation method will be considered if it is possible and empirically worth to do imputation of missing data.
Selection bias, information bias and confounding cannot be excluded.	Selection of participating medical institutions nationwide and enrollment of all patients who will receive blinatumomab prescriptions in the cycle 6 or later at the eligible institutions as much as possible during enrollment period without exclusion criteria. Analysis results will be interpreted with caution, acknowledging the limitations, whether or not appropriate statistical methods could be applied to address the bias.

10. Protection of Human Subjects

The study protocol is reviewed and approved by the local regulatory agency, PMDA as well as external ethical committee (EC). The study and data collection are conducted in accordance with the Pharmaceutical and Medical Device Act, GPSP and Helsinki Declaration. Local Medical Act provides the physician and co-medical 'Confidentiality Obligation' of patients that is set forth in the study agreement between the representatives of study site and Amgen Astellas BioPharma K.K.

Before registering the patient to this study, physician informed the patient about the aim, method, and potential risk of the study and utilization of the patient's data in keeping individual patient's information unidentified.

11. Collection, Recording, and Reporting of Safety Information and Product Complaints

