11.2 Safety Collection, Recording and Submission to Amgen Requirements

This study is collecting information from investigators prospectively at a point in survey. All safety events (adverse events, product complaints, and other safety findings) considered to have occurred following patient exposure to blinatumomab will be

collected during observational study period from start of cycle 6 administration to final study contact with the exception of the protocol-exempted events listed below. The investigator is responsible for recording safety events that they become aware of during study period in the patient's appropriate study documentation. Collected safety events must be submitted as individual safety reports to Amgen Astellas BioPharma K.K. via the Safety Reporting Form (paper form) provided by the Safety Department of Amgen Astellas BioPharma K.K. promptly.

Protocol Exempted Events

CTCAE grade ≤ 2 events are not required to be individually reported or collected in the study. If any of the exempted events have a fatal outcome, they should be considered a serious adverse event and must be collected and reported individually to Amgen Astellas BioPharma K.K. promptly. All safety information that is not specified in this section is to be collected and submitted to Amgen Astellas BioPharma K.K. promptly. Protocol-exempted events and safety events that are suspected to be related to any medicinal product other than Blinatumomab should be reported to the local authority in line with the local country requirements.

See [Appendix C](#) for sample Safety Report Form(s) and [Appendix E](#) for sample Pregnancy and Lactation Notification Worksheets. The Investigator may be asked to provide additional information for any event submitted, which may include a discharge summary or extracts from the medical record. Information provided about the event must be consistent with information recorded in the study documentation where safety data may also be recorded.

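### Late registration is allowed but everyone is counted from the start of cycle 6, so deaths before the patient is informed drop out of the incidence

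*Protocol*

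**What the plan says.** Four rules in the protocol interact.

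- **Who may enter, and when.** Section 9.2 says: "This study targets the patients who started the blinatumomab cycle 6 therapy before concluding the contract with medical institutions, as well". The inclusion criterion in 9.2.3.1 is: "Patients for whom blinatumomab is prescribed in the cycle 6 or later at medical institutions". No latest registration date relative to cycle 6 Day 1 is set.
- **What entry requires.** Section 10 says: "Before registering the patient to this study, physician informed the patient about the aim, method, and potential risk of the study". The registration items in 9.3.3 include "date of informed, start date of cycle 6 blinatumomab administration". No route is described for a patient who has already died.
- **Time zero.** Section 9.2.6 says: "Each patient will be followed from the beginning of cycle 6 to the end of cycle 9". Under section 11.2, safety events are "collected during observational study period from start of cycle 6 administration to final study contact".
- **What is done about selection.** Section 9.9 names selection bias in general terms and answers it with "enrollment of all patients who will receive blinatumomab prescriptions in the cycle 6 or later", as far as possible. Sections 9.7.2.5.3 and 9.7.2.5.4 plan no sensitivity analysis. The near-zero loss to follow-up expected in 9.7.2.2 concerns patients already registered.

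The Abstract, 9.3.4 and 9.9 call the study prospective, and the design schema places registration ahead of the cycle 6 Day 1 column.

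**The concern.** When the clock starts before entry is possible, a patient must survive the gap to be counted at all. This is delayed entry with immortal time. Someone who dies in the gap leaves both numerator and denominator. Someone who survives it and registers late enters the denominator as a patient observed from cycle 6 Day 1. Enrolling as many patients as possible does not cure this, because effort cannot make a patient who has died informable.

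The gap can be long. If each cycle runs to Day 84 as in the schema, a patient registered at the start of cycle 9 brings in up to 3 × 84 = 252 of 4 × 84 = 336 days that had to be survived first.

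At stake is the primary result: the incidence of grade 3 or higher events per safety specification, which section 9.5 intends to set beside study 00103311. Missing early deaths would lower the survey's figure and could read as reassurance.

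**Working it through.** **1. The plan's own figure.** Section 9.5 says 40 patients give 95% confidence of at least one case when the true incidence is 8% or more.

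- P(at least 1) = 1 − 0.92^40 = 0.964, so the statement holds.
- The smallest sufficient n is ln(0.05)/ln(0.92) = 35.9, that is 36.
- The smallest incidence that 40 patients cover at 95% is 1 − 0.05^(1/40) = 7.2%.
- The reference incidences also reproduce: 3/36 = 8.3%, 8/36 = 22.2%, 6/36 = 16.7%.

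**2. A model for late entry.** Let p be the true incidence and f the share of eligible patients who could be registered only after cycle 6 Day 1. Let q be the excess probability that such a patient, having had the event, is lost before being informed. Late start is taken as unrelated to the event. Then

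observed incidence = p(1 − fq) / (1 − pfq).

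The protocol gives neither f nor q. The values below are assumptions chosen to show a range.

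| f | q | fq | true 8% seen as | P(≥1 of 40) | true 16.7% seen as | true 22.2% seen as |
|---|---|---|---|---|---|---|
| 0 | any | 0 | 8.0% | 96.4% | 16.7% | 22.2% |
| 0.10 | 0.25 | 0.025 | 7.8% | 96.1% | 16.3% | 21.8% |
| 0.25 | 0.50 | 0.125 | 7.1% | 94.7% | 14.9% | 20.0% |
| 0.50 | 1 | 0.50 | 4.2% | 81.8% | 9.1% | 12.5% |

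Example, third row at 8%: 0.08 × 0.875 / (1 − 0.08 × 0.125) = 0.0700/0.990 = 7.1%.

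The last row is an extreme. Deaths before registration do have q = 1, but applying q = 1 to a whole event category means that every late-starting patient with that event is lost before being informed.

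**3. Where the 95% statement breaks.** Setting the observed incidence to 7.2% with p = 8% gives fq = (0.08 − 0.0722)/(0.08 × (1 − 0.0722)) ≈ 0.106. Below that product the claim in 9.5 survives late entry; above it, it does not.

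**4. Direction.** For deaths before registration the loss is certain. For non-fatal events q can be zero, or negative if event-free patients leave more often.

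**The case against.** The strongest reply is that the pre-contract sentence in 9.2 widens capture towards all cycle 6 starters and was not meant to select survivors. Registered late entrants do not lose their earlier events either: 11.2 collects from the start of cycle 6, and 9.4 makes medical records the source. Both points stand, so only unregistered patients can cause under-counting. That entry requires a living patient is itself inferred from the informing step in section 10; the protocol does not say so in terms.

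Stronger readings are tempting, but the documents do not carry them.

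- *Transplanted or transferred patients are shut out too.* A reader might infer this, but no text bars them. Section 9.2.6 ends follow-up the day before transplantation; it does not prevent registration. Event-free patients lost through transplant would push the incidence up.
- *The study-size section is contradicted.* It speaks of "The collection of 40 subjects who transition to cycle 6". Someone in cycle 7, 8 or 9 has also made that transition, so there is no conflict.
- *Late entry must be common.* About 250 sites for 40 patients is 0.16 per site, but that does not show when contracts are signed. Some patients are expected to continue from survey 20170655 and may be known before cycle 6.
- *The bias is large.* Suppose 25% to 50% of the 40 are late entrants, and 10% to 20% of all late starters had the event and cannot be registered. Then 10 × 0.10/0.90 = 1.1 to 20 × 0.20/0.80 = 5.0 patients are missing, and an observed 22.2% corresponds to a true 24.3% to 30.8%. With one true incidence for on-time and late starters, this requires 1.11/2.70 = 41% to 5.0/7.71 = 65% of late starters with the event to be unregistrable. At an observed 8.3% the same inputs require 93% and 108%; the latter is impossible.

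It can also be said that tabulation by lag is analysis-plan detail, and that the survey is descriptive with a general caution in 9.9. This stands in part. The entry rule and time zero are, however, fixed in the protocol, and the caution does not mention delayed entry. A shift smaller than sampling error (the exact 95% interval for 9/40 is 10.8% to 38.5%) is still a bias, which the interval does not show.

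**Conclusion.** The structural point holds. Late registration, informing first and counting from cycle 6 Day 1 together leave deaths in the gap uncounted, and nothing in the protocol measures or repairs this. The direction is certain only for those deaths. For non-fatal grade 3 or higher events it is conditional on differential departure from care.

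The size is unknown: zero if nobody registers late, slight in the mild assumed case and substantial only in the extreme one. Counts are small, however. At 8.3%, 40 patients are expected to yield 0.083 × 40 = 3.3 event patients, so losing one would remove about 30% of the expected count. A reader might infer that the primary result is known to be materially biased; the protocol does not support that. The sample-size arithmetic is correct. This is something the sponsor should fix because the fix is cheap, not a defect that must be cured before the survey can be used.

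**What to change.** - In 9.7.2.4, compute for each patient the lag from the cycle 6 start date to the date informed, both on the registration form under 9.3.3. Present the grade 3 or higher incidences for all patients, and separately for on-time and late entrants. On-time means informed on or before cycle 6 Day 1, or within a short window fixed in advance; a window leaves a small residue of the same problem.
- Base the comparison with 00103311 on the on-time group, or show both.
- State delayed entry in 9.9 as a specific limitation, with its certain direction for early deaths and uncertain direction otherwise.
- Where feasible, report how many known cycle 6 starters at participating sites were not registered, with vital status. Survey 20170655 might help identify them, but its protocol is not at hand and not every patient continues from it.

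Counting late entrants' person-time only from the date informed would not be enough, because the endpoint in 9.7.2.4 is the number and proportion of patients with events.

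The cost is a few sentences of protocol text, one derived variable and, for the last item, a short site log. The on-time table will hold fewer than 40 patients if some register late, with wider intervals, and the detection statement in 9.5 then applies to that smaller number.
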